Interviews will continue until saturation of themes in each set of patient, relative and health provider interviews. This is anticipated to occur after up to 15-20 interviews in each set have been undertaken and 10-12 interviews for the service commissioners and other stakeholders

Economic models

As this study is primarily aimed at developing new economic models for FH identification and management informed by evidence synthesis, using FH databases, and conducting qualitative interviews, no sample size calculation is required.

ADVERSE EVENTS

The occurrence of an adverse event as a result of participation within this study is not expected and no adverse event data will be collected.

ETHICAL AND REGULATORY ASPECTS

Page 22 of 31

Evaluating protocols for identifying and managing patients with FH. Protocol. Final Version 2.0 8 June 2017

For the qualitative study, interviews may take place at participants' homes and other sites across the country. The researchers will follow the University of Nottingham Lone Working Policy when working off-site.

It is not anticipated that the interviews will raise any sensitive issues, however should this occur, the researcher will inform the Chief Investigator who will take appropriate action (e.g. inform the clinical care team if required).

ETHICS COMMITTEE AND REGULATORY APPROVALS

The study will not be initiated before the protocol, consent forms and participant information sheets have received approval / favourable opinion from the Research Ethics Committee (REC), and the respective National Health Service (NHS) or other healthcare provider's Research & Development (R&D) department and the Health Research Authority (HRA) if required. Should a protocol amendment be made that requires REC approval, the changes in the protocol will not be instituted until the amendment and revised informed consent forms and participant information sheets (if appropriate) have been reviewed and received approval / favourable opinion from the REC and R&D departments. A protocol amendment intended to eliminate an apparent immediate hazard to participants may be implemented immediately providing that the REC are notified as soon as possible and an approval is requested. Minor protocol amendments only for logistical or administrative changes may be implemented immediately; and the REC will be informed.

The study will be conducted in accordance with the ethical principles that have their origin in the Declaration of Helsinki, 1996; the principles of Good Clinical Practice, and the Department of Health Research Governance Framework for Health and Social care, 2005.

For databases, the researchers will follow all requirements set out by provider as described in the data sharing agreements (where available). Research will be conducted in accordance to information governance guidelines set forth by the respective Caldicott Guardian.

INFORMED CONSENT AND PARTICIPANT INFORMATION

For the qualitative study, the process for obtaining participant informed consent will be in accordance with the REC guidance, and Good Clinical Practice (GCP) and any other regulatory requirements that might be introduced. The investigator or their nominee and the participant shall both sign and date the Consent Form before the person can participate in the study.

The participant will receive a copy of the signed and dated forms and the original will be retained in the Study records.

The decision regarding participation in the study is entirely voluntary. The investigator or their nominee shall emphasize to them that consent regarding study participation may be withdrawn at any time without penalty or affecting the quality or quantity of their future medical care (for the patient participants), or loss of benefits to which the participant is otherwise entitled. No study-specific interventions will be done before informed consent has been obtained.

The investigator will inform the participant of any relevant information that becomes available during the course of the study, and will discuss with them, whether they wish to continue with the study. If applicable they will be asked to sign revised consent forms.

Page 23 of 31

Evaluating protocols for identifying and managing patients with FH. Protocol. Final Version 2.0 8 June 2017

If the Consent Form is amended during the study, the investigator shall follow all applicable regulatory requirements pertaining to approval of the amended Consent Form by the REC and use of the amended form (including for ongoing participants).

For the databases, the researchers will only access anonymised data with no identifiable information, thus no informed consent is needed.

RECORDS FOR QUALITATIVE STUDY

Study Forms

For the qualitative study, each participant will be assigned a study identity code number, for use on study forms, other study documents and the electronic database. The documents and database will use a study identifier which includes a site identifier starting from 01 and a participant number starting from 01. For example, 0101 or 0205.

Study forms will be treated as confidential documents and held securely in accordance with regulations. The investigator will make a separate confidential record of the participant's name, date of birth and Participant Study Number, to permit identification of all participants enrolled in the study, in case additional follow-up is required.

Study forms shall be restricted to those personnel approved by the Chief or local Investigator and recorded as such in the study records.

All paper forms shall be filled in using black ballpoint pen. Errors shall be lined out but not obliterated by using correction fluid and the correction inserted, initialled and dated. The Chief or local Investigator shall sign a declaration ensuring accuracy of data recorded in the study forms.

Source documents

Source documents shall be filed at the investigator's site and may include but are not limited to, consent forms, study records, field notes, interview transcriptions and audio records. A study form may also completely serve as its own source data. Only study staff shall have access to study documentation other than the regulatory requirements listed below.

Direct access to source data / documents

The study forms and all source documents shall made be available at all times for review by the Chief Investigator, Sponsor's designee and inspection by relevant regulatory authorities.

DATA PROTECTION

All study staff and investigators will endeavour to protect the rights of the study's participants to privacy and informed consent, and will adhere to the Data Protection Act, 1998. The study forms will only collect the minimum required information for the purposes of the study. Study forms will be held securely, in a locked room, or locked cupboard or cabinet. Access to the information will be limited to the study staff and investigators and any relevant regulatory authorities (see above). Computer held data including the study database will be held securely and password protected. All data will be stored on a secure dedicated web server. Access will be restricted by user identifiers and passwords (encrypted using a one way encryption method).

Page 24 of 31 Evaluating protocols for identifying and managing patients with FH. Protocol. Final Version 2.0 8 June 2017

Electronic data will be backed up every 24 hours to both local and remote media in encrypted format.

For analysis, interview transcripts will be shared with the partner organisations (University of Southampton, University of York, Cardiff University and University Hospitals Southampton NHS Foundation Trust). Transcripts will have identifiable personal data removed and will only include participant identifier and the type of participant (index patient, family member, provider, commissioner or stakeholder). These will be shared in password protected files via email with the password telephoned to the relevant contact at each organisation separately.

QUALITY ASSURANCE & AUDIT

INSURANCE AND INDEMNITY

Insurance and indemnity for clinical study participants and study staff is covered within the NHS Indemnity Arrangements for clinical negligence claims in the NHS, issued under cover of HSG (96)48. There are no special compensation arrangements, but study participants may have recourse through the NHS complaints procedures.

The University of Nottingham as research Sponsor indemnifies its staff, research participants and research protocols with both public liability insurance and clinical trials insurance. These policies include provision for indemnity in the event of a successful litigious claim for proven non-negligent harm.

STUDY CONDUCT

Study conduct may be subject to systems audit for inclusion of essential documents; permissions to conduct the study; CVs of study staff and training received; local document control procedures; consent procedures and recruitment logs; adherence to procedures defined in the protocol (e.g. inclusion / exclusion criteria, timeliness of visits); accountability of study materials and equipment calibration logs.

STUDY DATA

Monitoring of study data shall include confirmation of informed consent; source data verification; data storage and data transfer procedures; local quality control checks and procedures, back-up and disaster recovery of any local databases and validation of data manipulation. The Study Coordinator/Academic Supervisor, or where required, a nominated designee of the Sponsor, shall carry out monitoring of study data as an ongoing activity.

Entries on study forms will be verified by inspection against the source data. A sample of study forms (10% or as per the study risk assessment) will be checked on a regular basis for verification of all entries made. In addition the subsequent capture of the data on the study database will be checked. Where corrections are required these will carry a full audit trail and justification.

Study data and evidence of monitoring and systems audits will be made available for inspection by the REC as required.

Page 25 of 31 Evaluating protocols for identifying and managing patients with FH. Protocol. Final Version 2.0 8 June 2017

RECORD RETENTION AND ARCHIVING

In compliance with the ICH/GCP guidelines, regulations and in accordance with the University of Nottingham Code of Research Conduct and Research Ethics, the Chief or local Principal Investigator will maintain all records and documents regarding the conduct of the study. These will be retained for at least 7 years or for longer if required. If the responsible investigator is no longer able to maintain the study records, a second person will be nominated to take over this responsibility.

The study documents held by the Chief Investigator on behalf of the Sponsor shall be finally archived at secure archive facilities at the University of Nottingham. This archive shall include all anonymised audio recordings, study databases and associated meta-data encryption codes.

DISCONTINUATION OF THE STUDY BY THE SPONSOR

The Sponsor reserves the right to discontinue this study at any time for failure to meet expected enrolment goals, for safety or any other administrative reasons. The Sponsor shall take advice as appropriate in making this decision.

STATEMENT OF CONFIDENTIALITY

Individual participant medical or personal information obtained as a result of this study are considered confidential and disclosure to third parties is prohibited with the exceptions noted above.

Participant confidentiality will be further ensured by utilising identification code numbers to correspond to treatment data in the computer files.

Such medical information may be given to the participant's medical team and all appropriate medical personnel responsible for the participant's welfare.

If information is disclosed during the study that could pose a risk of harm to the participant or others, the researcher will discuss this with the CI and where appropriate report accordingly.

Data generated as a result of this study will be available for inspection on request by the participating physicians, the University of Nottingham representatives, the REC, local R&D Departments and the regulatory authorities.

PUBLICATION AND DISSEMINATION POLICY

In the UK, we are active current contributors to NICE guidelines for FH and will ensure the outputs of this cost-effectiveness analysis inform updated NICE guideline recommendations and quality standards.

We will also work with the International FH foundation, US CDC Office of Public Health Genomics and European collaborators, and our international advisers in Australia, USA and Europe to ensure our analysis informs international guidelines recognising potential differences between international settings.

We will ensure that findings are highlighted to the public, patients, and policymakers (NHS, Department of Health, Public Health England and NICE) in partnership with third sector voluntary organisations (Heart UK and British Heart Foundation - BHF). Page 26 of 31

Evaluating protocols for identifying and managing patients with FH. Protocol. Final Version 2.0 8 June 2017

We will support Heart UK to organise patient and health professional focus groups to help refine findings and produce digital dissemination strategies (e.g. involving website, email, Facebook, Twitter or similar).

Working closely with Heart UK and BHF we will disseminate learning from the study to NHS commissioners by:

- Networking with existing and potential FH service commissioners across England, e.g. national NHS commissioners workshop
- Presenting study findings in a way that makes sense to managerial and commissioning audiences, e.g. publish articles in NHS professional and health service commissioner journals
- Sharing learning of early implementers of FH services
- Scoping the possibility of producing a FH toolkit incorporating advice on FH service design and a revised costing template for FH services that is generalizable to the English NHS, based on CCG geographies.

As well as completing NIHR HTA monograph, standard dissemination strategies, of peerreviewed open access primary care, public health, cardiovascular and genetic publications and conference presentation, will be further prioritised.

USER AND PUBLIC INVOLVEMENT

We have an established and experienced Familial Hypercholesterolaemia (FH) PPI group involved across our research processes from identifying questions to dissemination [3]. This includes working with nominated lay representative by Heart UK; local service user who has FH and have experienced cascade testing; and national PPI Co-Applicant [name], who has FH, was a member of the NICE FH Guideline Group [20] and is experienced in the development and dissemination of patient information resources.

Although it is 8 years since NICE guidelines for FH, our PPI group know there is minimal improvement in the identification of this condition. They consider current protocols are not working and that cascade testing could be improved. They strongly support direct contact with all relatives.

To assess the acceptability of testing protocols, our PPI group has highlighted the need for qualitative investigation with patients, health professionals and FH patient champions. With HeartUK and BHF, we continue to review current protocols and testing. We will ensure our PPI group continues to inform and be actively involved in the proposed work.

Patients and the public will be involved throughout this study, from design of the research through to management of the research, supporting developing participant information, contributing to the reporting of the research and in dissemination of the findings.

STUDY FINANCES

Funding source

This study is funded by the National Institute for Health Research (NIHR) Health Technology Assessment (HTA).

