Identification in primary care remains poor and opportunistic. Processes in both primary and specialist care are neither systematic nor well documented, and strict criteria for genetic testing prevail. Subsequent cascade testing of relatives is also sub-optimal due partly to perceived barriers for specialists to approach relatives directly, particularly if they live in different geographies. Moreover, people with FH are mainly managed by specialist care, despite the potential for greater management in primary care.

Existing cost -effectiveness analyses (UK and internationally) have explored whether or not specific protocols for cascading are cost-effective [8,9,10,11]. However, commissioners and policy makers are uncertain about whether current cascade programmes represent the best value for money in practice [12,13]. They have questioned whether tighter criteria for cascading could offer better value for money, and whether service protocols could do more to maximise the number of relatives tested.

By using robust and multiple data sources, and modelling a wide range of possible protocols for cascade testing, this study will identify the most cost-effective protocol for cascade testing for familial hypercholesterolaemia in UK clinical practice and the NHS.

The study will use economic modelling to evaluate the cost-effectiveness of alternative cascade testing protocols. Parameters to inform these models will be derived from existing published literature and routinely available data in primary and specialist care. In this study we will collect data from 3 large regional FH services (Wessex, Scotland, Wales) with differing protocols for cascade testing.

The Welsh service, serving a population of 3.2 million since 2011 and co-funded by BHF, identifies new FH cases using modified Dutch Lipid Clinic referral criteria [16], including triglyceride levels. Several modalities of identification are used including specialist nurses accessing primary care records. Cascade testing to relatives is offered directly (initiated by

```
Page 11 of 31
```

Evaluating protocols for identifying and managing patients with FH. Protocol. Final Version 2.0 8 June 2017

the clinic/medical professionals) and indirectly (initated by patients providing information to their family members).

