The Wessex service, serving a population of 2.5 million, is one of the first British Heart Foundation (BHF) pilots (2014). Cases are identified through primary care based FH coordinators using modified NICE Simon-Broome referral criteria with higher LDL cholesterol threshold (>5.5) and takes account of triglyceride levels [14]. Cascade testing to relatives is usually through indirect contact.

The Scottish service protocol [15] serves a population of 5.5 million since 2008. GPs use NICE Simon-Broome criteria for referring suspected index cases either directly for genetic testing or through a network of 17 lipid clinics. Patients with genetically confirmed FH are referred to genetic services for cascade testing, initially contacting relatives indirectly, but more recently using indirect and direct approaches.

All 3 services have paediatric FH diagnosis protocols: Wessex and Scotland offer genetic tests from 10 years of age whilst the Welsh service offer testing from 8 years of age.

In exploring and identifying the most cost-effective protocols and care pathways, successful future and wider implementation will be dependent on their acceptability to a range of stakeholders. Exploration of the experiences, views and attitudes of patients and family members, primary care and specialist health providers, and service commissioners is thus needed.

STUDY OBJECTIVES AND PURPOSE

PURPOSE

The study will identify the most cost-effective and acceptable protocol for FH cascade testing based on best current evidence. In this cost-effectiveness model, aspects of the cascade protocol will be varied in different combinations to generate a series of protocols for comparison. Protocols will differ in terms of the criteria used to select individuals with FH from whom to cascade (e.g. Simon-Broome, Dutch Lipid Clinic referral criteria, cholesterol thresholds), methods of testing (genetic, LDL), direct or indirect contacting of relatives, how far to test family (1st, 2nd, 3rd degree relatives etc.) and extension of testing to relatives in other geographical areas.

PRIMARY OBJECTIVE

To evaluate the cost-effectiveness of alternative protocols for FH cascade testing using data from service protocols in three UK regions, the literature, and linkage of national clinical databases.

SECONDARY OBJECTIVES

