Once all of the interviews are complete we would like to send a copy of the interview preliminary findings to all participants who wish to receive this. A sample of these may have

Page 16 of 31

Evaluating protocols for identifying and managing patients with FH. Protocol. Final Version 2.0 8 June 2017

opted on the consent form to agree to a short telephone interview to discuss the findings. This telephone interview will be arranged by the researcher with the participant. Written notes will be made during the call.

Economic models

The primary objective involves developing an economic model that synthesises evidence on cascade testing, with evidence on the short- and long-term costs and benefits of identifying and managing FH cases. This will be based on anonymous data from a) differing cascade testing services operating in three geographical areas of the UK; and b) linking UK primary and secondary care datasets describing the management and outcomes of patients with FH alongside data from the peer-reviewed and grey literature.

The model will compare alternative cascade testing protocols to each other. The testing compared will differ by:

- criteria used to select individuals with FH from whom to cascade (e.g. Simon-Broome, Dutch Lipid Clinic referral criteria),
- methods of testing (genetic, LDL),
- direct or indirect contacting of relatives,
- how far to test family (1st, 2nd, 3rd degree relatives etc.)
- extension of testing to relatives in other regions.

The model will predict for each protocol:

- yield of FH relatives;
- reduction in long term cardiovascular events,
- survival and quality adjusted life years (QALYs) due to lipid lowering therapy initiation at different ages;
- short- and long-term costs incurred by the NHS and personal social services.

Routine NHS service databases

Data on yield of FH cases will be captured from routine service datasets in 3 areas: Wales, Wessex and Scotland. This rich evidence to estimate the impact of identifying and managing relatives with FH will enhance the precision and robustness of cost-effectiveness model parameters.

Access to the routine NHS service databases/data will be requested from the relevant NHS or university bodies with approval from the appropriate regulatory authorities (e.g. Health Research Authority, NHS ethics) and R&D offices.

Wales PASS (FH) data

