- 4) charting: extracting data from its original context, summarising and grouping it in chart form according to the thematic reference,
- 5) mapping and interpretation: reviewing the charts and research notes to compare and contrast, search for patterns and connections and provide explanations for the emerging findings.

Validate findings: To further refine and validate analysis, all participants will be invited to review and comment on summaries of preliminary findings to enable further opportunity to reflect on findings.

Economic models

Page 20 of 31

Evaluating protocols for identifying and managing patients with FH. Protocol. Final Version 2.0 8 June 2017

Analysis of routine NHS databases

To generate the parameters necessary to populate the cascading process module of the economic model, routine service data collected in PASS and Scottish FH datasets will be analysed.

Data from these datasets will be used to predict the probability that an individual with specific demographic and clinical characteristics will have FH. This analysis will use data on all individuals with possible FH who received a genetic test in Scotland, Wales and Wessex to date. This analysis will use logistic regression to develop a predictive model to quantify the probability that an individual carries a monogenic mutation. This analysis will facilitate the comparison of different criteria by which index cases are selected for genetic testing and subsequent cascading. These criteria will range from broad (all index cases tested) through to tight criteria (only those with the highest probabilities of carrying the monogenic mutation are genetic tested).

Data will also be used to identify the potential number of relatives per index case, the actual number of relatives contacted and tested, and the characteristics of those relatives. The demographic and disease characteristics of the relatives will be used to generate predictions of their long-term outcomes. This data will also provide information on the extent of lipid lowering treatment use in relatives prior to FH diagnosis. This is important as it will impact upon the benefit of diagnosis.

Analysis of linked-FH databases

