1st or also more distant relatives, inclusion of relatives in other geographical areas). The model will predict for each protocol: the yield of FH relatives; the reduction in long term cardiovascular events and extensions to survival and QALYs due to lipid lowering therapy initiation at different ages; and short- and long-term costs incurred by the NHS and personal social services. The ultimate output of the model will be the incremental cost-effectiveness ratios (ICERs) corresponding to the simultaneous comparison of all evaluated protocols. These results will be interpreted using a range of cost-effectiveness thresholds to identify a cost-effective FH protocol.

The results will be subject to deterministic and probabilistic sensitivity analysis. The deterministic sensitivity analyses will examine areas of parameter and structural uncertainty identified during the modelling process, including sensitivity analyses examining the impact of adherence, the approach used to model the impact of diagnosis and treatment on outcomes, and the impact of having a nationally co-ordinated programme compared to individual region-specific services as this will impact on the yield of relatives contacted and ultimately tested. Value of information analysis will be conducted to quantify the overall value of future research in this area, and the value of specific future research designs (e.g. a comparison of direct and indirect testing, improved data on treatment adherence and the link between adherence and outcomes).

Model review and validation

A series of established steps will be conducted to establish model validity [18]. The model outputs will be reviewed by the expert group who reviewed the conceptual model to establish face validity. This will take the form of a one-day meeting. At this meeting findings from the qualitative research will be reviewed to identify whether this has any implications for the feasibility of the protocols evaluated. Verification (technical validation) will be conducted using standard methods; cross-validation via comparison with other models will be conducted, as will external validation with other sources of data on outcomes in FH patients.

Sample size and justification

Qualitative study

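### No costed no-cascade strategy is listed among the compared options, so the model can rank cascade protocols but cannot show that the chosen one is worth its cost

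*Protocol*

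**What the plan says.** The set of strategies is described in four places in the Protocol, and the description is consistent.

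- **Study objectives and purpose, Purpose:** "aspects of the cascade protocol will be varied in different combinations to generate a series of protocols for comparison".
- **Study regimen, Economic models:** "The model will compare alternative cascade testing protocols to each other". The five listed dimensions are the criteria for choosing whom to cascade from, the test, direct or indirect contact, the degree of relative, and extension to other regions.
- **Analyses, Analysis of routine NHS databases:** "These criteria will range from broad (all index cases tested) through to tight criteria", the tight end being the cases most likely to carry a mutation. The range does not extend to testing nobody.
- **Analyses, Model programming:** the output is the "incremental cost-effectiveness ratios (ICERs) corresponding to the simultaneous comparison of all evaluated protocols", followed by the decision rule: "These results will be interpreted using a range of cost-effectiveness thresholds to identify a cost-effective FH protocol". The threshold values are not given.

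The Study background and rationale gives the motive, that "commissioners and policy makers are uncertain about whether current cascade programmes represent the best value for money in practice", and the aim, that "this study will identify the most cost-effective protocol for cascade testing for familial hypercholesterolaemia in UK clinical practice and the NHS".

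No section names no cascade testing, opportunistic detection alone, or current practice as a strategy in the comparison.

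**The concern.** A cost-effectiveness threshold tests whether extra health is worth its extra cost relative to the next best use of the money. If every option in the set is a form of cascading, the ICERs price the step from one cascade protocol to a dearer one. They do not price the step from no cascading to the first protocol. Some cascade protocol is then selected at every threshold, whatever its net benefit against doing none.

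This bears on the primary objective. The planned decision rule is a statement about value, not only about rank, and the Publication and dissemination policy says the results will be used to inform NICE recommendations. The probabilistic and value-of-information analyses inherit the same set. Probabilities of being cost-effective would be shared among cascade protocols only, and the value of further research would leave out uncertainty about whether to cascade at all.

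**Working it through.** The Protocol states no cost, QALY, ICER or threshold value, so there is no figure of its own to reproduce. The check is of the logic, on assumed inputs. All figures below are assumptions.

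**Formulas.** ICER = difference in cost ÷ difference in QALYs. Net monetary benefit (NMB) = threshold × QALYs − cost, with no cascade set at zero cost and zero QALYs.

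**Example 1, per index case.** Protocol A, the cheapest cascade, against none: +£400, +0.010 QALY. Protocol B against A: +£100, +0.008 QALY. So B against none: +£500, +0.018 QALY.

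- A against none: 400 / 0.010 = £40,000 per QALY
- B against A: 100 / 0.008 = £12,500 per QALY
- B against none: 500 / 0.018 = £27,778 per QALY

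| Threshold | NMB of A | NMB of B | Chosen from {A, B} | Chosen from {none, A, B} |
|---|---|---|---|---|
| £20,000 | 200 − 400 = −£200 | 360 − 500 = −£140 | B | none |
| £30,000 | 300 − 400 = −£100 | 540 − 500 = +£40 | B | B |

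With no cascade in the set, A is extendedly dominated (£40,000 for the first step, £12,500 for the second), and B is judged at £27,778. The two sets therefore give different decisions at every threshold below £27,778 and the same decision above it.

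**Example 2, totals against none.** A: £400k, 10 QALYs. B: £600k, 15 QALYs. B against A: 200k / 5 = £40,000. From {A, B}, A is chosen by default at £15,000, £20,000 and £30,000, although A against none is 400k / 10 = £40,000. With no cascade included, neither is chosen at those thresholds.

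**Example 3, cascading is good value.** A: £80k, 10 QALYs. B: £150k, 16 QALYs. A against none: 80k / 10 = £8,000. B against A: 70k / 6 = £11,667. B against none: 150k / 16 = £9,375. B is chosen at £15,000, £20,000, £30,000 and £50,000 with or without no cascade. The omission changes nothing.

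The effect thus ranges from none to a reversed decision. Which case applies depends on the ICER of the chosen protocol against no cascade, and the planned set does not produce that quantity.

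**The case against.** The strongest reply is that the question is deliberately one among cascade protocols. The background notes that earlier economic evaluations examined whether particular cascade schemes are cost-effective. It then asks about best value, tighter criteria and reaching more relatives. A ranking answers those questions, and that ranking is valid. But the Protocol does not report what the earlier evaluations found, so it does not establish that cascading beats no cascading. It also applies thresholds, which a ranking alone does not need.

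A second reply is that the Study configuration section limits the document's focus to the interviews and data extraction, and that a conceptual model or analysis plan may list more comparators. It is true that a no-cascade option is omitted rather than excluded. Even so, the Protocol itself states the decision set, in the same terms each time, and ties the conclusion to it.

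Four stronger readings are tempting but not supported:

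- **That the cheapest protocol having no ICER is itself a fault.** The least costly option never has one. Adding no cascade would normally move that role to no cascade.
- **That the predicted reduction in events has no reference.** The Protocol ties it to starting lipid-lowering therapy, collects relatives' treatment before diagnosis, and plans a scenario and sensitivity analyses on the impact of diagnosis. An undiagnosed counterfactual for outcomes is implied. What is missing is its listing as a costed strategy.
- **That the recommendation will be wrong.** Example 3 shows it need not be, and in Example 1 the reversal disappears at £30,000. The Protocol plans a range of thresholds.
- **That the repair needs no new input.** Treatment status before diagnosis does not give the rate at which relatives would be found without cascading.

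**Conclusion.** The point holds in a limited form. The listed strategies are all cascade protocols, yet their ICERs are to be judged against absolute thresholds. The plan supports a ranking among cascade protocols. It does not support the further statement that the one chosen is worth its cost, and it will select one even if its net benefit against no cascade is negative.

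The size cannot be stated from the Protocol. On the assumed figures of Example 1, £12,500 per QALY within the planned set corresponds to £27,778 against no cascade, which reverses the decision at £20,000 and leaves it unchanged at £30,000. The conclusion rests on the strategy set being as listed. If a no-cascade option is already intended, saying so settles the matter.

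**What to change.** In Study regimen, Economic models, and in Analyses, Model programming, state that a no-cascade strategy is included with its own costs and QALYs. Define it as the index case managed, with relatives detected and treated only at the background rate. Include it in the fully incremental, probabilistic and value-of-information analyses.

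For background treatment, use the data on relatives' lipid-lowering use before diagnosis that the routine-database analysis already plans to extract. For background detection, take a rate from the literature or assume one, and vary it in sensitivity analysis.

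The cost is a short addition to the text, one more arm in a model that is being built anyway, and one more uncertain parameter. Naming the current protocols of the three services as comparators would help readers but is optional, since their main features are already model dimensions.
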